10. DATA COLLECTION

10.1. CONSTRUCTS AND MEASURES

Clearly articulate the constructs of interest, measures to evaluate those constructs, and specific data collection instruments. Provide any information on the reliability and validity of the data collection instruments. For standardized instruments, you may provide the citation for the instrument.

Measure	Sample	Variable Type	Data source(s)	Variable Name	Definition
Co-parenting relationship behaviors	Has at least one child age 24 or younger	Continuous (range from 1 to 5 where 1 is strongly disagree and 5 is strongly agree)	nFORM entrance, OLLE follow-up	Copar_Beh	Average of 11 survey items that relate to positive interactions with the mother of participant's youngest child
Parenting relationship behaviors	Has at least one child age 24 or younger, saw child within past month	Continuous (range from 1 to 5 where 1 is never and 5 is every day or almost every day)	nFORM entrance, OLLE follow-up	Par_Beh	Average of 10 to 11 survey items (depending on child age) that relate to frequency of positive interactions with participant's youngest child
Parenting relationship attitudes	Has at least one child age 24 or younger, saw child within past month	Continuous (range from 1 to 5 where 1 is always and 5 is never)	nFORM entrance, nFORM exit	Par_Att	Average of 6 survey items that relate to frequency of feelings about participant's youngest child
Parenting relationship behaviors	Has at least one child age 24 or	Continuous (range from 1 to 5 where 1 is	nFORM entrance, ,	Parent_Fight	Reported frequency of

	younger, saw child within past month	never and 5 is every day or almost every day)	OLLE follow-up		fighting with child
Partner relationship behaviors	All survey respondents	Continuous (range from 1 to 5 where 1 is never and 5 is always)	OLLE pre-survey, OLLE post-survey, OLLE follow-up	Partner_Fight	Reported frequency of fighting with partner
Partner relationship behaviors	All survey respondents	Continuous (range from 1 to 5 where 1 is never and 5 is always)	OLLE pre-survey, OLLE post-survey, OLLE follow-up	Partner_Disagree	Average of 7 survey items related to frequency of disagreement with partner on different topics

* you may add rows by hitting the tab button, or right click and select insert row below

10.2. CONSENT

Describe how and when program applicants will be informed of the study and will have the option of agreeing (i.e., consenting to) or declining to participate in the study.

Staff present the purpose and benefits of standard and enhanced TCD services at orientations held at partner sites and the ASF mini clinic to recruit eligible fathers. Orientations also discuss the impact study and explain informed consent before soliciting participation. Participant responsibilities are clarified at the orientation, such as providing contact information and responding to surveys.

Program staff follow a protocol approved by IRB Solutions, Inc to solicit informed consent. Candidates are informed about study specifics and afterward can ask questions and seek clarification before documenting their consent. Candidates are made aware of their responsibilities to attend TCD service workshops and fulfill important requests, such as providing contact information and responding to surveys. In return, potential study participants are assured that receiving TCD services does not depend upon consent to participate in the study, their identifying information is kept confidential, and study results are reported at the group level to protect their anonymity. Project staff also inform candidates that incentives are offered for participating in TCD services and the study as follows:

Attendance Incentives:

- \$25.00 e-gift card for attendance at workshops 1 – 3.
- \$25.00 e-gift card for attendance at workshops 4 – 6
- \$25.00 e-gift card for attendance at workshops 7 – 9

- \$25.00 e-gift card for attendance at workshops 10 – 12

Program completion incentives:

- \$150.00 e-gift card for program completion plus TYRO Champion T-shirt, Champion Dad T-shirt, TYRO Pin and Certificate of Completion
- ASF also offers various wristbands displaying positive personal characteristics at various times based on participant engagement and group input.

Survey Completion Incentives:

- \$50.00 Giftogram gift card for OLLE Follow-up Survey.

10.3. METHODS OF DATA COLLECTION

If the evaluation will collect multiple waves of data, describe the timing of these waves below. When describing follow-up periods, specify whether the follow-up period will be post-baseline, post-random assignment, or post-program completion.

Wave of Data Collection (e.g., baseline, short-term follow-up, long-term follow-up)	Timing of Data Collection
Baseline	Collected immediately following informed consent and enrollment – during orientation or before first primary workshop session
Post-test	Collected after the completion of the primary services programming – during or following the last workshop or session
Follow-up (6 months after enrollment)	Collected approximately six months after program enrollment

For each measure, describe how data will be collected detailing which data collection measures will be collected by which persons, and at what point in the programming or at what follow-up point.

Measure	Timing of Data Collection (baseline, wave of data collection)	Method of Data Collection	Who Is Responsible for Data Collection?	Impact Evaluations Only: Will Methods or Collection Procedures Differ by Study Group?	Administrative Data Only: Will data access require data sharing agreement?
On-line Local Evaluation (OLLE) and nFORM Baseline Survey	Baseline	Participant self-enters survey using online data collection program or on paper surveys if necessary	CQI Data Manager will proctor data collection and assist participants as necessary	No	
OLLE and nFORM Post-Test Survey	Post-Test (approx. 12 weeks after enrollment during last workshop session)	Participant self-enters survey using online data collection program or on paper surveys if necessary	CQI Data Manager will proctor data collection and assist participants as necessary	No	
OLLE Six Month Follow-up Survey	Six months after enrollment / baseline	Participant self-enters survey using online data collection platform and link – or – Phone interview data collection	MER Research Staff/ participant tracking team	No	

* you may add rows by hitting the tab button, or right click and select insert row below

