7. IMPACT EVALUATIONS ONLY: METHODS TO DEVELOP STUDY GROUPS

If the research design includes the comparison of two or more groups (e.g., a program group and a comparison group), please specify how the groups will be formed and describe the programming for which each will be eligible and how they differ below. The control/comparison group and the program/treatment group should be assigned using a systematic approach appropriate to the research design. Note: If the research question(s) and study design do not necessitate comparisons, this issue does not need to be addressed.

Specify how the groups will be formed.

Study groups will be formed using IRB approved procedures for random assignment after enrollment into the TCD. After soliciting informed consent, participants who agree to participate in the study provide case managers with signed consent forms. After documenting consent, the CQI Data Manager randomly assigns participants to achieve an even distribution across the treatment and control groups. *Assignments are made and then recorded onto the nFORM data collection system by selecting cards*

	
that are organized into a stack that equals the number of parents who attended an orientation and now wish to receive TCD services and participate in the impact study. Cards in the stack have equal amounts of even and odd numbers depicted on them and one is drawn for each study participant. Selections into either the treatment or control group depended on whether a participant receives an even or odd number.

Please describe the comparison/control group experience – that is, the types of services available to the comparison/control group.
	
Fathers assigned to the control group do not receive enhanced TCD services. Instead, they receive the same standard services—TYRO Dads and Core Communication—and support services as treatment group parents under a shared condition (see the theory of change logic model mentioned above). Standard TCD service experiences for the control group should be the same as the treatment group. Parents assigned to both groups are offered the same number, schedule, and duration of workshop offerings for TYRO Dads and Core Communication curricula and attend them together, so they experience the same instructional practices that deliver the same curricula content.

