7.1. RANDOM ASSIGNMENT TO DEVELOP STUDY GROUPS

If groups will be constructed by random assignment, please describe the process of random assignment and how random assignment will be monitored to prevent crossover of those assigned to specific study groups (e.g., individuals assigned to the comparison group who receive treatment) by addressing the questions below.

Who will conduct random assignment?	Eligible fathers who wish to participate in the study are randomly sorted into a treatment or control group by the CQI data manager or by case managers under supervision of the CQI Data Manager. The CQI Data Manager is trained by Senior staff and overseen by a Senior Consultant from MER.
When does random assignment occur (e.g., before or after enrollment)?	Orientation attendees who express interest in TCD services return the following week to enroll at their respective recruitment sites. Those who are also willing to participate in the impact study provide signed consent forms before they are assigned to study groups. After consent is documented, parents are randomly sorted into either a treatment or control group.
How and when are study participants informed of their assignment status?	Participants will be informed of their assignment status immediately after randomization.
Will groups be stratified in any way to ensure balance between treatment and control? If yes, what characteristics or methods will be used?	No.
What strategies will be used to ensure there is no re-assignment or non-random assignment to the treatment group?	A C2 (i.e., client profile) is entered onto nFORM to create a client profile for eligible parents who attend orientations for the TCD Project. Parents who return to participate in the study have their study group assignment entered onto nFORM. Only parents assigned to the treatment group as noted on nFORM can register and attend Ray of Hope workshops. Study group assignment cannot be changed once it has been noted on nFORM.

What strategies will be used to minimize crossovers?	The nFORM system produces an operational report that specifies study group assignment for all parents who agree to participate in the study. Study group assignment as noted on nFORM will be examined with the relevant operational report during CQI-Team meetings to make sure participants receive the services specific to their study group.

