TYRO Champion Dads

Statistical Analysis Plan

12/9/2024

Clinicaltrial.gov ID:
NCT05256992

1. Data Analysis

Briefly describe the planned approach for data analysis. If an impact analysis is proposed, name the key dependent and independent variables, and describe any methods to minimize Type I error (i.e., finding positive impacts by chance) such as limiting the number of impacts to be analyzed and/or multiple comparison correction. Describe proposed approach(es) for addressing missing data.

Identify impact study sample

The impact study sample includes participants who: 1) were eligible to be randomized based, 2) gave recorded informed consent to be part of the study and randomly assigned to a treatment group, and 3) took both an entrance and exit and/or follow-up survey. The CONSORT diagram in Appendix A shows exclusion criteria and the anticipated size of the overall impact study sample, which we anticipate to differ for attitudinal items that will use wave 2 data vs behavioral questions that will use wave 3 data. The analytic sample for particular outcome measures will vary based on missing data.

Defining analysis measures

For each outcome construct, we have identified the relevant measures from nFORM that are theoretically aligned with that construct. We will generate a correlation matrix between items in a given construct to ensure that theoretically related items are also empirically related in our data set. Items that are not strongly correlated with other items in a construct will be removed as necessary. Factor analysis will be used to ensure that all construct items hang together (using an alpha of 0.7 or higher as the threshold).

Once we are confident that all of the items align with a given construct, we will create a composite measure by taking an average of the scores on each non-missing item in the construct. The measure definition matrix below provides information on each proposed outcome measure.

For the sake of consistency and simplicity, parenting and co-parenting analyses will use a participant's youngest child as the focal child.

Measure	Sample	Variable Type	Data source(s)	Variable Name	Definition
Co-parenting relationship behaviors	Has at least one child age 24 or younger	Continuous (range from 1 to 5 where 1 is strongly disagree and 5 is strongly agree)	nFORM entrance, OLLE follow-up	Copar_Beh	Average of 11 survey items that relate to positive interactions with the mother of participant's youngest child

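### The plan lets the baseline surveys be completed after fathers know their arm, although those surveys help decide who is analysed and which covariates are used

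*Protocol*

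**What the plan says.** **Baseline timing.** Protocol section 10.3 describes the baseline wave as "Collected immediately following informed consent and enrollment", and gives its window as "during orientation or before first primary workshop session".

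**Assignment and disclosure.** Protocol section 7.1: "Orientation attendees who express interest in TCD services return the following week to enroll at their respective recruitment sites". Then: "After consent is documented, parents are randomly sorted into either a treatment or control group". On disclosure: "Participants will be informed of their assignment status immediately after randomization".

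**Who does what.** Under Protocol section 7, "the CQI Data Manager randomly assigns participants to achieve an even distribution across the treatment and control groups"; section 7.1 adds that case managers may do so under that role's supervision. For the baseline and post-test surveys, section 10.3 states that the "CQI Data Manager will proctor data collection and assist participants as necessary".

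**How the analysis uses baseline.** The SAP (Identify impact study sample) admits only consenting, eligible fathers who "took both an entrance and exit and/or follow-up survey". Under Handling missing data, a single-item outcome also drops any father without a pre-survey answer to that item. Under Analytic approach, baseline characteristics and starting attitudes and behaviours are compared between arms, and those that differ become covariates. The SAP describes these starting points as preceding services. It does not say that they precede randomisation.

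**The concern.** Consent is the reference point for both baseline and assignment, and neither document says which of the two comes first. The outer limit of the baseline window, the first primary workshop, can fall after fathers have been told their arm.

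The trial is open to this kind of influence. It is unblinded, and the arms differ only in a domestic-violence curriculum. The baseline items include self-reported fighting with a child and fighting and disagreement with a partner (Protocol section 10.1). The role that makes or supervises assignment also proctors the survey.

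A baseline taken after disclosure could reach the estimate by two routes.

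- **Exclusion.** A father who learns his arm and does not complete the entrance survey leaves the impact sample even if he later supplies an outcome. If that happens unequally by arm, the analysed groups are no longer the randomised groups.
- **Adjustment.** If knowledge of the arm shifts reported baseline, a detected difference is entered as a covariate. The model then removes from the outcome comparison a difference that assignment itself produced.

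**Working it through.** **1. The plan's own figure.** Protocol sections 9.2 and 9.3 give 310 analysed per arm (620 in total), one-tailed alpha 0.05, 80% power and a minimum detectable effect of 0.2 SD.

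- SE of a difference in means, in SD units: √(2/310) = 0.0803.
- Minimum detectable effect: (1.645 + 0.842) × 0.0803 = 0.1997.

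The stated 0.2 reproduces, so it is used below as the yardstick. The timing issue does not change it.

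**2. Order of steps, side by side.**

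| Step | Stated timing | Source |
|---|---|---|
| Consent | At enrolment, the week after orientation | Protocol 7.1 |
| Assignment | After consent is documented | Protocol 7, 7.1 |
| Disclosure of arm | Immediately after assignment | Protocol 7.1 |
| Baseline surveys | Immediately after consent and enrolment, with a window to the first primary workshop | Protocol 10.3 |

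Both consent–baseline–assignment and consent–assignment–disclosure–baseline fit these statements. Section 10.3 also allows baseline during orientation, although section 7.1 puts consent and enrolment a week later, so the table does not settle the order.

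**3. Adjustment route.** These inputs are assumptions, not figures from the documents: baseline-to-outcome slope b = 0.5; arm-related shift in reported baseline s = 0.05, 0.1 or 0.2 SD; baseline differences tested at two-sided 0.05 with 310 per arm.

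*If baseline is always a covariate*, the size of the bias is b × s:

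- 0.5 × 0.05 = 0.025 SD (0.025/0.2 = 12.5%)
- 0.5 × 0.1 = 0.05 SD (25%)
- 0.5 × 0.2 = 0.10 SD (50%)

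*Under the SAP's rule*, baseline enters only when a difference is detected. Write the observed baseline difference as s + e, where e is chance imbalance with SE 0.0803.

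- Detected: the covariate enters and the bias has size b × s.
- Not detected: there is no adjustment, but these samples tend to be those where e offset the shift, and that imbalance carries into the outcome.

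Expected bias = b × { s × P(detected) − E[e; not detected] }, where E[e; not detected] = 0.0803 × { φ(−1.96 − s/0.0803) − φ(1.96 − s/0.0803) } and φ is the standard normal density.

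| s | P(detected) | s × P | E[e; not detected] | Expected bias | Share of 0.2 |
|---|---|---|---|---|---|
| 0.05 | 0.095 | 0.0048 | −0.0120 | 0.5 × 0.0168 = 0.008 | 4% |
| 0.10 | 0.238 | 0.0238 | −0.0246 | 0.5 × 0.0484 = 0.024 | 12% |
| 0.20 | 0.702 | 0.1404 | −0.0278 | 0.5 × 0.1682 = 0.084 | 42% |

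With a positive slope the bias has the opposite sign to the shift. The documents do not indicate which way a shift would go.

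**4. Exclusion route.** Suppose the arms lose shares dT and dC of fathers with outcome data because baseline is missing, and those lost differ from those kept by g SD. The bias is (dT − dC) × g. With assumed losses of 10% v 5% and g = 0.3, it is 0.05 × 0.3 = 0.015 SD. With 15% v 5% and g = 0.5, it is 0.10 × 0.5 = 0.05 SD. The documents give no figure for any of these inputs.

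**The case against.** The strongest reply is that this is an unstated order, not a demonstrated fault. The step described as immediate after consent is the baseline survey, whereas assignment is only said to follow documented consent. The card stack is sized to the group wishing to take part (Protocol section 7), which suggests a batch draw with time for surveys beforehand. This stands. A reader might infer that assignment follows consent directly, that both steps occur at one contact, or that baseline answers were in fact given with knowledge of the arm. The documents support none of these.

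A reader might also take slope times shift as the bias to expect. That figure applies only if baseline is always adjusted for. Under the SAP's selection rule the expected bias is smaller, by a factor of about three for the smallest shift assumed.

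The mechanism is unproven too. Orientation describes both service packages to everyone (Protocol section 10.2), fathers referred because of a domestic violence case are excluded (section 3), and collection procedures are the same in both arms (section 10.3). These points lower the likelihood of a shift but do not rule one out.

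The SAP's non-response section compares response rates by arm and aims to adjust for threats to validity. That may reveal unequal completion, but it names no method of adjustment and cannot detect shifted scores. A father who leaves before the entrance survey may also miss later surveys, so the entrance rule may remove few additional fathers. That number is unknown.

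Finally, planned study enrolment ended on 11-30-2024 (section 3) and local baseline surveys on 05/31/24 (section 4), both before the SAP date of 12/9/2024. Re-ordering the steps is therefore largely moot. The retrospective check is not.

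**Conclusion.** The concern holds as a permitted risk. The plan allows baseline surveys after disclosure of the arm, and the SAP uses those surveys both to define the impact sample and to choose covariates. It does not show that any baseline was late or that any answer was affected.

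If some were, the expected adjustment bias runs from about 0.008 to 0.084 SD (4% to 42% of the 0.2 SD minimum detectable effect) over the assumed shifts of 0.05 to 0.2 SD. It rises to 0.025 to 0.10 SD if baseline is always adjusted for. These figures apply the shift to the whole arm; if only some baselines were late, the average shift would be smaller. The exclusion route does not depend on covariate selection, and its size depends on counts the documents do not give. The outcomes concerned are confirmatory and the check is cheap, so the sponsor should make it.

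**What to change.** - **Any father still to be enrolled:** require the nFORM entrance and OLLE pre-surveys to be submitted before the card is drawn.
- **Fathers already enrolled:** compare the dates (and times, where recorded) of the ACS, entrance and OLLE pre-surveys with the assignment date, and report late and missing baselines by arm. The ACS must be included, because the timeline in Protocol section 4 lists it with the other baseline surveys and no section places it before assignment.
- **SAP:** add a sensitivity analysis that adjusts only for covariates recorded before assignment and keeps fathers who have outcome data but a late or missing baseline.

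The cost is one date check and one extra analysis. The planned sample size, power and minimum detectable effect are unaffected. If the dates show that baseline preceded assignment, a sentence saying so in the report closes the point.

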10.4. ENSURING AND MONITORING DATA COLLECTION

Describe plans for training data collectors and for updating or retraining data collectors about procedures. Detail plans to regularly review data that have been submitted and to assess and swiftly address problems.

This evaluation will utilize both post-program surveys (completed at the completion of core programming) and follow-up surveys collected six months after enrollment. The methods for these data collections differ. The primary driver for post-program survey completion is high rates of program retention. This data point will be collected during the last workshop session. As such, only those individuals who complete the program and who are at the data collection session will be likely to participate in the post-program data collection.

All program staff and evaluation staff will undergo a rigorous set of trainings to prepare for the evaluation. All staff receive an overview and introductory training to present the goals and objectives of the evaluation effort and its importance to the overall project. Next, all staff receive training on human subject protection and are required to pass a certification test on the subject matter. All staff will also receive a detailed training on the evaluation, including the evaluation tools, timing and data collection process, and the role and importance of randomization of participants.

In addition, the data manager and the primary local evaluation staff will undergo a rigorous training process to better understand the context of HMRF research, training on data collection procedures they will be responsible for, and training on the nFORM system and use of nFORM data in a CQI process. MER is creating networks of CQI data managers and Evaluation Project Managers across the 12 projects that we are evaluating so that all staff have access to experienced data managers and evaluation staff who have done this work previously. This training takes the form of weekly training sessions that are currently underway.

Members of the CQI team will also receive specific training on the MER CQI process that has been developed prior to the launch of data collection or program services. As described elsewhere, MER is assisting the program staff in implementing a robust CQI process that will focus on retention as one of the primary areas of program improvement, and as such, we are anticipating relatively modest levels of attrition for this data collection.

On a bi-weekly basis, the data manager, the local evaluation staff, and MER technical specialists will be responsible for downloading data from the nFORM and MER On-Line Local Evaluation (OLLE) systems for processing and presentation to the CQI team for tracking and monitoring performance measurement outcomes (recruitment, enrollment, dosage, completion, referrals, etc.) so that near real-time adjustments can be made to program implementation to ensure compliance with program goals and objectives.

All MER training is currently being recorded, and as new staff come on board with projects or project staff turnover (or need refresher training), recorded training material can be shared and accessed with follow-up one on one training with the primary local evaluator and the MER Line of Business Lead.

